Opioids were the most frequently used method to control orthopedic pain. However, multiple complications has been encountered with the use of opioids in elderly patients such as delirium, hypotension, respiratory depression, prolonged hospital stay or post-discharge side effects as addiction or dependence ^[7]. Fentanyl can be considered the most suitable among different opioids due to its potency, rapid onset, short duration and minimal depressive effect on respiration ^[8].

Regional nerve blocks can efficiently reduce pain associated with hip fracture, with rapid-onset, site-specific analgesia that is more effective than standard systemic analgesia alone. There is also moderate evidence that nerve blocks contribute to reduce rates of delirium, and some suggestion of reduced length of inpatient stay, morbidity and mortality^[9]. Therefore, regional analgesia provides a safer alternative for opioids with even stronger analgesia and fewer complications. The use of regional analgesia is not limited to operation room (O.R), it can be started from the emergency department to facilitate patient examination, transportation and radiological investigations ^[10].

With ultrasound guidance, regional analgesia became easier, more accurate, more specific and requires less amounts of local anesthetic. Regional analgesia for hip fractures was strongly recommended by both pain management pathway by Health Quality Ontario ^[11] and by the evidence based guidelines published by the American Pain Society, the American Society of Regional Anesthesia and Pain Medicine and the American Society of anesthesiologists ^[12].

There is multiple techniques to provide analgesia for hip fractures through peripheral nerve block while patient in supine position including femoral nerve block, 3-in-1 block, fascia iliaca block, intraarticular injections and local anesthetic infiltration in soft tissues surrounding surgical site (the last is suitable for postoperative pain) ^[13].

One method widely used to provide regional analgesia for hip fractures is ultrasound guided Fascia Iliaca block in which local anesthetic is injected between fascia iliaca and psoas muscle to block femoral, obturator and lateral cutaneous nerves ^[14].

Recently, the anterior capsule was found to be the richest part of the hip joint in nerve supply. A recent anatomical study by Short et al. stated that the femoral nerve (FN) and obturator nerve (ON) consistently provided innervation to the anterior hip capsule. They also found that the accessory obturator nerve (AON) is present in higher percentage of the specimens than previously suggested (54% vs. 8%-29%). When the AON is present, it contributes innervation to the anterior capsule. The key point of that study was that the articular branches of these three nerves to the anterior hip capsule have a constant relationship to the space between the anterior inferior iliac spine (AIIS) and iliopubic eminence that can be used as a potential site for radiofrequency ablation in case of osteoarthritis ^[15].

Girón et al. in 2018 used the previous anatomical description to develop a new technique using ultrasonography to block the articular branches to the anterior capsule of the hip at the point they cross the iliopectenial eminence, they called it the pericapsular nerve group (PENG) block. ^[16].

Rationale

Pain is a major problem that has to be dealt with in case of hip fracture, as it resembles an obstacle for examination, positioning for receiving neuroaxial anesthesia and postoperative mobility and physiotherapy.

With the introduction of ultrasound in regional anesthesia and peripheral nerve blocks, regional analgesia float to the surface as a substitute for opioids with less side effects. Of the many techniques to provide regional analgesia for hip fractures; fascia iliaca block was widely used with good results. In 2018 Pericapsular Nerve Group Block was introduced to provide regional analgesia for hip fractures with interesting results.

Up to our knowledge ultrasound guided pericapsular nerve group block was not used before in Zagazig university hospitals for pre- and post-operative analgesia in elderly patients with hip fracture.

Research Question

Which is more effective as an ultrasound guided regional analgesic technique for pre- and post-operative analgesia in elderly patients with hip fracture, Pericapsular Nerve Group Block or Fascia Iliaca block?

Hypotheses

Null hypothesis:

There is no difference between ultrasound guided Pericapsular Nerve Group Block and ultrasound guided Fascia Iliaca Block as a regional analgesic techniques for pre- and post-operative analgesia in elderly patients with hip fracture.

Alternative hypothesis:

There is a difference between ultrasound guided Pericapsular Nerve Group Block and ultrasound guided Fascia Iliaca Block as a regional analgesic techniques for pre- and post-operative analgesia in elderly patients with hip fracture.

Aim of the work

The aim of the present study is to improve quality of pain control in the pre- and post-operative periods in elderly patients with hip fracture.

Objectives

1. To compare the time of performance and the analgesic effect in the pre- and post-operative periods between ultrasound guided Pericapsular Nerve Group (PENG) block, fascia iliaca block and intravenous fentanyl (control group).
2. To assess the quality of patient's positioning during performance of spinal anesthesia by operator satisfaction score.
3. To assess time of onset of postoperative ambulation.

Patients and Methods

I. Technical design:

● **Site of the study:**

This study will take place at Zagazig University Hospitals after approval of Institutional Review Board (IRB).

● **Duration of the study:**

Two years.

● **Sample size:**

Assuming that mean \pm SD for VAS scores at positioning for spinal anesthesia in intravenous fentanyl versus fascia iliaca block were 3.5 ± 2.5 versus 2.1 ± 0.9 [4] with confidence level 95% and power of test 80%.

The total sample size is 51 (17 in each group) calculated by OpenEpi[®].

● **Inclusion criteria:**

1. Patient acceptance.
2. Accepted mental state of the patient.
3. Gender: both sexes.
4. Age above 65 years old.
5. Body mass index 18.5-35 kg/m².
6. ASA physical status II and III.
7. Unilateral hip fracture assigned for surgical fixation.
8. Expected duration of surgery \leq 3 hours.

● **Exclusion criteria:**

1. Associated trauma or multiple fractures.
2. Peripheral neuropathy.
3. Coagulopathy.
4. Infection at site of injection.
5. Allergy to the drugs used in the study.
6. Advanced kidney, liver or heart disease.

- **Withdrawal criteria:**

The patient has the right to withdraw from the study at any time without any negative consequences on their medical or surgical treatment plan.

II. Operational design:

- **Type of the study:**

This study is a randomized double-blind controlled clinical trial.

- **Parameters of the study:**

All patients will be visited on the day before surgery at the ward, for all patients a full history (personal, medical and family) will be taken, physical examination will be done. We will order a full laboratory work up: complete blood picture (CBC), kidney function tests (KFTs), liver function tests (LFTs), random blood sugar (RBS), prothrombin time (PT), partial thromboplastin time (PTT), international normalized ratio (INR), serum electrolytes and 12-lead ECG and the results will be revised. We will order any consultation required to prepare the patient (cardiology consultation will be done routinely).

Explanation of the whole procedure to the patient and a written informed consent will be obtained. Instructions will be given for preoperative fasting (6 hrs for light meals and 2 hrs for clear fluids). Visual analogue score for pain will be explained to all patients.

An intravenous cannula will be inserted for preoperative medications and blood sample will be sent for blood group matching to insure availability of blood of the same group before the operation.

On the day of surgery one hour before the operation, all patients will receive intravenous pantoprazole 40 mg and cefotaxime 1 gm.

On arrival to the operating room:

1. Monitoring: Standard operative monitoring will be applied to all patients including electrocardiogram (ECG), peripheral pulse oximeter and non-invasive blood pressure (NIBP). Basal readings of heart rate (HR), mean arterial pressure (MAP), oxygen saturation (SpO₂) and body temperature will be recorded.
2. Fluid preloading: Lactated ringer in a dose of 6 ml/kg over 30 minutes.
3. Revision on the resuscitation equipment including anesthetic machine, ventilator, face mask, oral airway, laryngeal mask, laryngoscope, endotracheal tubes, DC shock and drugs as atropine, ephedrine, hydrocortisone, antihistaminic, epinephrine and general anesthesia induction drugs.
4. Each patient will be asked for (his/her) pain by visual analogue pain score during rest and we will do the 15 degrees leg raising test and record VAS, heart rate and mean blood pressure both during rest and 15 degrees leg raising test. The records will be done by the anesthesiologist responsible for administration of spinal anesthesia and blinded to the groups' assignment.

● **Equipment:**

○ **Ultrasound:**

Mindray diagnostic ultrasound system, model: M5, SN: MR-55006765. Made in China.

○ **Transducers:**

- Mindray high frequency transducer, model: 10L4s, SN:MLW3C101256. Made in China.
- Mindray low frequency transducer, model: C5-2s, SN: NDX54023456. Made in China.

○ **Needle for performing the block:**

22-gauge, 80-mm Quincke spinal needle.

- **Needle for spinal anesthesia:**

25-gauge, Quincke spinal needle.

- **Local anesthetics:**

Bupivacain 0.5% diluted to 0.25% solution and magnesium sulphate as an additive for regional blocks and heavy bupivacaine 0.5% for spinal anesthesia.

- **Randomization:**

Patients will be randomly allocated by computer generated randomization table into three equal groups (17 patients each):

Group C (Control group):

Control group (n=17): Patients will be assigned to receive opioids analgesia before spinal anesthesia in the form of intravenous fentanyl in a dose of 1mic/kg divided into two boluses with 5 minutes interval in between before positioning the patient for spinal anesthesia.

Group P:

PENG block group (n=17): Patients will be assigned to receive Pericapsular Nerve Group Block (PENG Block) before positioning the patient for spinal anesthesia.

After disinfection of the skin from the anterior superior iliac spine (ASIS) to the inguinal ligament with alcohol on the affected side, sterile drapes will be used to surround the area of the block. While the patient in the supine position, a curvilinear low-frequency ultrasound probe (2–5MHz) will be first placed in a transverse plane over the anterior inferior iliac spine (AIIS), then rotated caudally about 45 degrees to be aligned with the pubic ramus. At this point the view on the screen will be viewing from medial to lateral; the pectineus muscle, the femoral artery, the iliopectineal eminence (IPE), the iliopsoas muscle and tendon and the AIIS. A 22-gauge, 80-mm spinal needle will be inserted from lateral to medial in an in-plane approach to place the tip in the musculofascial plane between the psoas tendon anteriorly and the pubic ramus posteriorly. After negative aspiration, the local anesthetic solution will be injected in 5-

mL increments while observing for adequate fluid spread in this plane for a total volume of 20 mL of 0.25% bupivacaine + 250 mg magnesium sulphate. A hypoechoic expanding shadow should be visualized between the psoas tendon and the pubic ramus indicating proper site of injection [16].

Group F:

Fascia Iliaca block group (n=17): Patients will be assigned to receive Fascia Iliaca Block (F.I Block) before positioning for spinal anesthesia.

After disinfection of the skin over the upper thigh with alcohol on the affected side, sterile drapes will be used to surround the area of the block. While the patient in the supine position, a linear high-frequency ultrasound probe (10–15MHz) will be placed in the inguinal crease to identify the femoral artery and vein in the short axis. Then the ultrasound probe will be slid laterally while identifying the psoas muscle until the most anterior position of the curve of the psoas muscle is identified. A 22-gauge, 80-mm needle is inserted and advanced using an in-plane technique until the tip of the needle is positioned at that point, noting the ‘pop’ through the fascia lata and fascia iliaca. A small test injection is made to ensure that the fluid is seen to lift the fascia iliaca and flow between the fascia and the psoas muscle. After negative aspiration, 30 mL of 0.25% bupivacaine + 250 mg magnesium sulphate is injected in 5 mL increments under ultrasound visualization, with repeating test aspiration after every 5 mL. An expanding anechoic collection just below the fascia iliaca separating it from the psoas muscle should be certainly visualized indicating correct placement of anesthetic solution [17].

In the three groups, the onset of analgesia will be detected by 15 degrees leg raising test and will be recorded. The 15 degrees leg raising test will be used after 10 minutes from injection of local anesthetic in the groups received regional analgesia and after 2 minutes from intravenous injection in the fentanyl group. While the patient is supine, we will try to passively elevate the patient’s leg on the affected side for 15 degrees. If the patient complains of intolerable pain on moving his leg, the test will be aborted and we will wait for a minute before repeating the test. The test will be repeated every minute until we detect the onset of the analgesia that will be represented by dynamic VAS ≤ 4 . For all patients visual analogue pain

score (VAS) is used to evaluate pain. VAS is done by drawing a 10cm vertical line on a piece of paper with its limits “no pain” (0) on one side and “extreme pain” (10) on the other side. The patient will be asked to point where the pain (he/she) experiences lies on the line and the score is recorded ^[18]. Patient will be asked to evaluate his pain on VAS scale before and after the analgesic technique (starting 10 minutes after regional blocks and repeated every minute and 2 minutes after fentanyl injection). Once $VAS \leq 4$, patient will be positioned to receive spinal anesthesia. Vital signs will be recorded with each VAS reading.

Administration of spinal anesthesia:

After analgesia is established and fluid preload is given, patient’s position will be changed to sitting position to receive spinal anesthesia. Spinal anesthesia will be administered by an anesthesiologist who is blinded to groups’ assignment.

Anesthesiologist’s satisfaction with patient’s positioning will be evaluated by operator satisfaction score ; 0=unsatisfactory, 1=satisfactory, 2=good or 3=optimal ^[4]. This scoring will be done by the anesthesiologist responsible for spinal anesthesia administration.

During patient positioning for spinal anesthesia, VAS and vital signs (HR, MAP, SpO₂ and body temperature) will be recorded. If a patient reports $VAS \geq 4$ during positioning, the procedure will be stopped, the patient will be recorded as a failure rate and 1 mic/kg of i.v. fentanyl will be administered in any group. Positioning will be reattempted after VAS is reduced to <4.

After patient is in the sitting position, sterilization of the skin of the back will be done by 10% betadine then sterile drapes are used to surround the area of injection. Then 2 cc of 2% lidocaine will be injected to anesthetize the skin and subcutaneous tissue by forming a skin wheel. Spinal anesthesia will be performed by paramedian approach in the intervertebral space (L3/L4) using a 25G Quincke spinal needle with the bevel directed laterally. After correct needle placement in the subarachnoid space which is confirmed by free flow of cerebrospinal fluid (CSF), 2.5 cc of 0.5% hyperbaric bupivacaine (12.5 mg) + 25 mic fentanyl will be

injected in the subarachnoid space and the needle will be extracted. The skin will be dressed and the patient will be placed in the supine position and oxygen will be supplied by a facemask.

Patient will be evaluated for the effect of spinal block regarding both sensory and motor blocks. Sensory level will be evaluated using pin prick. Motor block will be evaluated using the modified bromage scale. Patient is asked to elevate his extended lower limbs and the score is given as follows: ^[19]

Grade 0 = No motor block.

Grade 1 = Inability to raise extended leg; able to move knees and feet.

Grade 2 = Inability to raise extended leg and move knee; able to move feet.

Grade 3 = Complete motor block of the limb.

The surgery will be started after achieving grade 3 on modified bromage scale and sensory level reaching umbilicus (T10). Patients will be monitored for heart rate (HR), oxygen saturation (SpO₂), mean arterial blood pressure (MAP) and body temperature and recorded every 10 minutes till the end of operation. Patients will be also monitored for the possible side effects of the used techniques (spinal anesthesia, regional blocks and parenteral fentanyl).

- Possible complications of spinal anesthesia include hypotension (decrease in systolic blood pressure by >20% of basal value) and bradycardia (decrease in heart rate by >20% of the basal value). Hypotension will be treated by intravenous fluids and vasopressor (ephedrine bolus 5mg repeated after 3 minutes if needed) while bradycardia will be treated by 1 mg of atropine.
- The most feared complication of regional blocks is local anesthetic toxicity. It can be avoided by not exceeding the toxic dose (2-2.5 mg/kg for bupivacaine) and avoiding inadvertent intra-arterial injection by proper visualization of the needle and injected local anesthetic by ultrasound and aspiration test before every increment injection. Manifestations of toxicity includes tingling of the tongue, circumoral numbness, tinnitus, blurred vision, agitation, muscle twitches, convulsions and cardiovascular manifestations as hypotension, bradycardia, heart block and cardiac arrest. Treatment is mainly supportive (respiratory and cardiovascular support), cardiopulmonary

resuscitation in case of cardiac arrest and the antidote is intralipid 20% (1.5 ml/kg over 1 minute then infusion in a rate of 0.25 ml/kg/min).

- In the elderly parenteral fentanyl may cause delirium or respiratory depression. Delirium can be assessed using the confusion assessment method (CAM). The CAM diagnostic algorithm is based on four cardinal features of delirium: 1) acute onset and fluctuating course, 2) inattention, 3) disorganized thinking, and 4) altered level of consciousness. A diagnosis of delirium according to the CAM requires the presence of features 1, 2, and either 3 or 4 [20].

At the end of the procedure patient will be asked to evaluate the analgesic technique used by patient's satisfaction score: Patient will be asked to rate his satisfaction with the technique of analgesia used by giving a score on a 1-3 scale (1 = unsatisfactory analgesia, 2 = satisfactory analgesia, 3 = excellent analgesia) [21].

In the recovery room: Patient will receive 1 gm paracetamol and 30 mg ketorolac by intravenous infusion as a part of standard multimodal analgesia.

In the ward: Postoperative standard analgesia will continue in the form of 1gm paracetamol/8hours and ketorolac 30 mg/12hours. Patient will be monitored for vital signs (HR, MAP, SpO₂ and body temperature), time of offset of spinal anesthesia (time from end of intrathecal injection of hyperbaric bupivacaine till recovery of the lower limbs motor power indicated by achieving grade 0 on modified bromage scale and fine touch sensation indicated by sensing pin brick) and postoperative pain by VAS score. Vital signs and VAS will be recorded at 2, 4, 6, 12 and 24 hours postoperative.

If patient gives VAS \geq 4 or complains of intolerable pain, a rescue analgesia will be given in the form of nalbuphine 0.1 mg/kg. We will record time of first rescue analgesia (the time between complete injection of the local anesthetic in the regional groups or fentanyl injection and the first analgesia requested by the patient), total postoperative rescue analgesic consumption in first 24 hours and time of onset of postoperative ambulation.

• **Collecting data:**

From each patient the following data will be collected:

- Patient characteristics (name, age, gender, body mass index (BMI), ASA grade).
- Fracture type.
- Type and duration of surgery (time from end of skin preparation till suturing the wound).
- Physical examination (mental status, decubitus, chest, abdomen, neurological and examination of the site of injection), laboratory investigations (complete blood count, random blood sugar, international normalized ratio, prothrombin time, partial thromboplastin time, kidney functions tests, liver functions tests and serum electrolytes).
- Vital signs (heart rate, mean blood pressure, respiratory rate, temperature and SpO₂). Vital signs will be recorded before and after the analgesic technique, during positioning for spinal anesthesia and then every 10 minutes till the end of the surgery. Then we will record vital signs at 2, 4, 6, 12 and 24 hours postoperative.
- Intraoperative total fluids given, blood loss and urine output.
- Visual analogue pain score will be recorded before and after analgesic technique used (starting 10 minutes after regional blocks and repeated every minute and 2 minutes after fentanyl injection) and during positioning. VAS will be also recorded at 2, 4, 6, 12 and 24 hours postoperative.
- Time of block performance (time from the end of skin sterilization till end of injection of local anesthetic).
- Onset time of the analgesic technique (time from end of injection of local anesthetic or intravenous fentanyl till reaching VAS \leq 4) by 15 degrees leg raising test. The 15 degrees leg raising test will be used after 10 minutes in the groups received regional analgesia and 2 minutes in the fentanyl group. We will try to elevate the patient's leg for 15 degrees. If the patient complains of pain on moving his leg, the test will be aborted and we will wait for a minute before repeating the test.
- Patient's satisfaction score.
- Anesthesiologist satisfaction score for patient's positioning.
- Possible complications of spinal anesthesia, regional blocks and parenteral fentanyl.

- Time of first rescue analgesia (the time between complete injection of the local anesthetic in the regional groups or fentanyl injection and the first analgesia requested by the patient) and total postoperative rescue analgesic consumption in first 24 hours postoperative.
- Time of onset of postoperative ambulation (time from end of surgery till first ambulation by the patient).
- Duration of spinal anesthesia (time from end of injection of intrathecal hyperbaric bupivacaine till offset of spinal anesthesia effect detected by degree 0 on modified bromage score and return of fine touch detected by sensing pin bricks).

- **Statistical analysis:**

The statistical analysis will be performed using a Statistical Package for the Social Sciences (SPSS®) version 16 (SPSS Inc., Chicago, IL, USA) for windows 10 operating system. Quantitative data will be expressed as means \pm SD while Qualitative data will be expressed as numbers and percentages (%). A probability value (p-value) <0.05 is considered statistically significant.

Presentation of the statistical outcomes will be in the form of tables and graphs that will be performed using the “Microsoft Office Excel® 2013” program.

III. Administrative design:

- **Results:**

Collected data will be tabulated in tables and suitable graphs and analyzed according to standard statistical methods.

- **Discussions:**

Discussion will be done on results compared to related relevant literature and scientific researches.

- **Conclusion & Recommendations:**

They will be derived from the findings of the study.

References

1. **Parker M and Johansen A.** Hip fracture. *Bmj.* 2006;333(7557):27-30.
2. **Kowark A, Rossaint R and Coburn M.** General versus spinal anesthesia for the elderly hip fractured patient. *Current Opinion in Anesthesiology.* 2019;32(1):116-9.
7. **Helmerhorst GT, Vranceanu A-M, Vrahas M, Smith M and Ring D.** Risk factors for continued opioid use one to two months after surgery for musculoskeletal trauma. *JBJS.* 2014;96(6):495-9.
8. **Pasero C.** Fentanyl for acute pain management. *Journal of PeriAnesthesia Nursing.* 2005;20(4):279-84.

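### The hypotheses compare PENG with fascia iliaca, but the 17 per group and 80% power come from fentanyl versus fascia iliaca, and the 80% is supported for neither contrast

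*Protocol*

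**What the plan says.** The protocol's Research Question sets one block against the other: "Which is more effective as an ultrasound guided regional analgesic technique for pre- and post-operative analgesia in elderly patients with hip fracture", followed by the names of the PENG and fascia iliaca blocks. Under Hypotheses, the null reads "There is no difference between ultrasound guided Pericapsular Nerve Group Block and ultrasound guided Fascia Iliaca Block as a regional analgesic techniques", and the alternative opens "There is a difference between ultrasound guided Pericapsular Nerve Group Block and ultrasound guided Fascia Iliaca Block". Fentanyl appears in neither.

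Objective 1 is wider. It compares block performance time and analgesic effect across "ultrasound guided Pericapsular Nerve Group (PENG) block, fascia iliaca block and intravenous fentanyl (control group"), and ranks no pair of arms above another.

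The Sample size paragraph (I. Technical design) takes its inputs from a cited earlier study: "VAS scores at positioning for spinal anesthesia in intravenous fentanyl versus fascia iliaca block were 3.5 ± 2.5 versus 2.1 ± 0.9", "with confidence level 95% and power of test 80"%. It concludes: "The total sample size is 51 (17 in each group) calculated by OpenEpi". The protocol gives no PENG pain score, no PENG SD, no target difference between the two blocks and no equivalence margin.

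**The concern.** A power statement belongs to one contrast, one assumed difference and one assumed spread. Here the contrast under test is block versus block, while the power is quoted for block versus fentanyl. A reader who takes the 80% at face value will attach it to the hypotheses, where nothing in the protocol supports it.

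What is at stake is how the main result is read. If PENG and fascia iliaca do not differ significantly, the result will match a null worded as no difference, in a trial described as having 80% power. It could then be reported as showing that the blocks are equally effective. The protocol does not plan such a claim, so this is a risk. But no margin is set, and the stated power would lend the claim weight that the design does not provide.

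**Working it through.** **1. The protocol's own figure.** Inputs from the Sample size paragraph: means 3.5 and 2.1, so a difference of 1.4; SDs 2.5 and 0.9; 95% confidence; 80% power. Sidedness is not stated; two-sided is taken from the non-directional alternative.

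n per group = (s1² + s2²)(z₀.₉₇₅ + z₀.₈₀)² / difference²

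= (6.25 + 0.81) × (1.960 + 0.842)² / 1.96 = 7.06 × 7.849 / 1.96 = 28.3, so 29 per group, or 87 for three groups.

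The stated 17 per group (51 in total) is not reproduced. Variants tried at 80% power:

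| Variant | n per group |
|---|---|
| One-sided 5% | 23 |
| Mean of the two SDs (1.7), two-sided 5% | 24 |
| Mean of the two SDs (1.7), one-sided 5% | 19 |
| SD 0.9 in both arms, two-sided 5% | 7 |
| SD 2.5 in both arms, two-sided 5% | 51 |
| One-sided 10% | 17 |

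Only the last returns 17, and it conflicts with the stated 95% confidence.

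**2. Power at 17 per group for fentanyl versus fascia iliaca.** Standard error = √(7.06/17) = 0.644. Standardized difference = 1.4/0.644 = 2.17.

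- Normal approximation: Φ(2.172 − 1.960) = Φ(0.212) = 58%.
- Welch t-test (20.1 degrees of freedom, critical value 2.085, noncentral t): 54%.

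**3. What 17 per group delivers for PENG versus fascia iliaca.** Two-sample t-test, two-sided 5%, 32 degrees of freedom. With 80% power the detectable difference is 0.991 SD. The 95% interval half-width is 2.037 × SD × √(2/17) = 0.699 × SD. The only block SD in the protocol is 0.9, for fascia iliaca. Its use for PENG, the SDs of 1.5 and 2.5 for block arms (2.5 is the fentanyl SD), and the true differences of 0.5 and 1.0 points are all assumptions.

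| Common SD | Detectable at 80% (points) | 95% half-width (points) | Power, 0.5 points | Power, 1.0 point |
|---|---|---|---|---|
| 0.9 | 0.89 | 0.63 | 35% | 88% |
| 1.5 (assumed) | 1.49 | 1.05 | 16% | 47% |
| 2.5 (assumed) | 2.48 | 1.75 | 9% | 20% |

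For scale, the assumed fascia iliaca mean is 2.1 on a scale that starts at 0, so PENG could improve on it by at most 2.1 points.

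**The case against.** Four points can be made on the other side.

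- **The fentanyl contrast belongs to the trial.** Objective 1 includes it, so sizing on it is not foreign to the design. This stands, but Objective 1 is an unranked three-group comparison and does not carry the 80% over to hypotheses that omit fentanyl.
- **The block comparison may be well powered.** A reader might infer that the trial is too small for PENG versus fascia iliaca. The documents do not show that. With SD 0.9 in both arms, 17 per group gives 88% power for 1.0 point and 99% for 1.4 points. The low figures for 0.5 points depend on a difference chosen for illustration. This stands: power for the hypothesis is unjustified, not proven inadequate.
- **Two active blocks need not differ by less than block and fentanyl.** It is plausible that they do, since the protocol's introduction describes nerve blocks as more effective than systemic analgesia alone. But no PENG score is given, so it remains an assumption and the point does not rely on it.
- **No equivalence claim is planned.** A no-difference null is ordinary superiority wording, and interval reporting is often left to an analysis plan. A reader might infer that the sponsor means to conclude equality from a non-significant test; nothing in the protocol says so. The risk of misreading remains, because the power statement is fixed in this document and is wrong there.

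A further tempting reading is that the 80% is at least sound for fentanyl versus fascia iliaca. The protocol's own inputs contradict this.

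**Conclusion.** The point holds. The stated power is tied to a contrast that neither hypothesis names, and it is not achieved for that contrast: about 54% to 58% in place of 80%, with 29 per group needed where 17 are planned. These figures rest on the protocol's inputs and a two-sided 5% test.

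For PENG versus fascia iliaca no single correct sample size can be given, because the protocol supplies no PENG value or target difference. What can be said is that 17 per group detects 0.99 SD with 80% power. In VAS points this is about 0.9 if both arms have SD 0.9, and more if the spread is larger. The protocol neither states nor justifies a target of that size. The sample-size paragraph should be corrected; the possible misreading of a null result is a secondary risk.

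**What to change.** Amend the Sample size paragraph, leaving enrolment at 17 per group:

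1. Withdraw the 80% power claim for both contrasts.
2. For fentanyl versus fascia iliaca, state the achieved power of about 54% (Welch, two-sided 5%) under the quoted means and SDs.
3. For PENG versus fascia iliaca, state that 17 per group detects 0.99 SD with 80% power: about 0.9 VAS points if both SDs are 0.9, and about 1.5 or 2.5 points under SDs of 1.5 or 2.5, labelled as assumptions.
4. Keep PENG versus fascia iliaca as the hypothesis rather than rewriting it to match the calculation. Commit to reporting that difference with its 95% interval (expected half-width 0.63 points at SD 0.9, and 1.05 or 1.75 at the assumed SDs).
5. State that a non-significant result will not be read as equal effectiveness, since no margin is set.

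The cost is protocol wording only. The downside is that the stated power becomes less favourable.

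### The printed sample-size inputs require 29 or 30 patients per group, not 17; if the inputs are right, 17 per group gives about 54–58% power, not 80%

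*Protocol*

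**What the plan says.** The protocol sizes the trial under Patients and Methods, I. Technical design, Sample size. The endpoint and comparison are "VAS scores at positioning for spinal anesthesia in intravenous fentanyl versus fascia iliaca block". The means and SDs, taken from reference 4, "were 3.5 ± 2.5 versus 2.1 ± 0.9", and the error rates are given as "with confidence level 95% and power of test 80"%. The result is "The total sample size is 51 (17 in each group) calculated by" OpenEpi.

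The Randomization section (II. Operational design) fixes the same number: "Patients will be randomly allocated by computer generated randomization table into three equal groups (17 patients each").

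The protocol gives no other sizing input. It has no mean or SD for the PENG group, no statement that the test is one-sided, no dropout allowance and no multiplicity adjustment. The alternative hypothesis has no direction: "There is a difference between ultrasound guided Pericapsular Nerve Group Block and ultrasound guided Fascia Iliaca Block".

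**The concern.** The paragraph prints everything needed to repeat the calculation, and repeating it does not give 17. This is the protocol's only power statement and its only justification for 51 patients, and the statement cannot be true together with its own inputs.

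The stake depends on which figure is wrong. If an input was miscopied, the defect is a misprint and 17 may be adequate. If the inputs are as intended, the chance of missing the assumed difference is more than twice the stated 20%, and a non-significant result would be read as coming from a trial with 80% power when it did not.

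**Working it through.** **Inputs (Protocol, Sample size).** Fentanyl mean 3.5, SD 2.5. Fascia iliaca mean 2.1, SD 0.9. Difference 3.5 − 2.1 = 1.4. Confidence 95%, power 80%. Sidedness is not stated; two-sided is taken because the alternative hypothesis has no direction. Allocation is equal.

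**Attempt to reproduce 17.** For two means with unequal SDs,

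n per group = (z₀.₉₇₅ + z₀.₈₀)² × (SD₁² + SD₂²) / difference²

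- (1.960 + 0.842)² = 7.849
- 2.5² + 0.9² = 6.25 + 0.81 = 7.06
- 1.4² = 1.96
- n = 7.849 × 7.06 / 1.96 = 28.27, so **29 per group**, and 3 × 29 = 87 in total.

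With the t distribution, power at 29 per group is 79.6% (pooled) or 78.8% (Welch). At 30 it is 81.0% or 80.2%. The t-based answer is therefore **30 per group**, 90 in total. The stated 17 is not reproduced, and 51 is not the two-group total either (2 × 29 = 58).

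**Other readings, per group.**

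| Reading | Calculation | n |
|---|---|---|
| One-sided 5% | (1.645 + 0.842)² × 7.06 / 1.96 = 22.27 | 23 |
| Most favourable rounding of inputs (SDs 2.45 and 0.85, difference 3.55 − 2.05 = 1.5) | 7.849 × (2.45² + 0.85²) / 1.5² = 23.46 | 24 |
| One-sided and favourable rounding | 18.48 | 19 |
| Fascia iliaca SD set to 0 | 7.849 × 6.25 / 1.96 = 25.03 | 26 |
| Common SD 0.9 | two-sided | 7 |
| Common SD 1.7 (average of the two) | two-sided / one-sided | 24 / 19 |
| Common SD 2.5 | 7.849 × 12.5 / 1.96 = 50.06 | 51 |
| Bonferroni over three pairs | two-sided 0.05/3 | 38 |

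None gives 17. Unequal allocation gives 32 + 16 or 27 + 54, and the protocol specifies equal groups in any case. The common-SD 2.5 row gives 51 per group, the number the protocol prints as its total. That may be coincidence; nothing in the text shows that it is the origin.

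**What would give 17.** With the difference held at 1.4, the root-mean-square SD would have to be about 1.46 instead of the 1.88 implied by the printed values (√(7.06/2)). With the printed SDs, the difference would have to be about 1.81. A single changed input can do it: a fentanyl SD of 1.8 gives 7.849 × (1.8² + 0.9²) / 1.96 = 16.2, so 17. A changed fascia iliaca SD alone cannot, because even an SD of 0 needs 26.

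**Power at 17 per group if the inputs are right (two-sided 5%).**

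- Standard error = √(7.06 / 17) = 0.644; 1.4 / 0.644 = 2.17.
- Power: 58.4% (normal), 55.8% (pooled t), 54.3% (Welch). A simulation of 100,000 trials from normal distributions gave 56.2% (pooled) and 54.5% (Welch).
- Chance of missing the difference: 100% − 58.4% = 41.6% to 100% − 54.3% = 45.7%.
- Even one-sided, power is only 67–70%.
- Difference detectable with 80% power: 1.81 (normal), 1.86 (pooled t), 1.90 (Welch).
- Expected 95% confidence interval half-width: about 1.3 (1.31 pooled, 1.34 Welch), nearly as large as the assumed effect.

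**The case against.** The arithmetic itself is not open to dispute. Four points can fairly be made on the other side.

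- **A misprint is a real possibility.** A fentanyl SD of 1.8 in place of 2.5 reproduces 17 exactly. This does not show that 1.8 is the right value, and the cited study is not available here. It does mean that an underpowered trial is possible but not shown. This point stands in full.
- **A three-group calculation might have been used.** A one-way analysis of variance needs about 61–81 patients in total if the PENG mean equals the fascia iliaca mean. If the PENG mean is assumed to be 1.4 and the common SD 1.88, it needs about 48. A PENG mean somewhat above 1.4 could therefore lead to 51. But the protocol gives no PENG mean and describes a two-group comparison, so this route needs an input that is not in the document.
- **The protocol names no test.** The normal, pooled t and Welch figures are approximations, and VAS data with such unequal SDs may not be normal. This is a reason to say about 55% and not to quote a decimal. It does not bring the required number near 17.
- **Enlarging the trial is also a remedy.** If the inputs stand, 29 or 30 per group would restore the stated power. That is correct. Restating the power is enough to make the protocol consistent, but only if the lower power is accepted.

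**Conclusion.** The point holds and must be fixed. The printed inputs require 29 per group (normal approximation) or 30 (t-test), against 17 stated, and no reading close to the text gives 17. The disagreement is certain; which figure is wrong cannot be settled from the protocol.

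The loss of power depends on the printed inputs being correct, a two-sided 5% comparison of fentanyl with fascia iliaca, and approximately normal data. On those assumptions, power for a difference of 1.4 is 54–58% instead of 80%.

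**What to change.** 1. Check the two means and SDs against reference 4 and the saved OpenEpi output. If an input is misprinted, correct it and show that the corrected value gives 17.
2. If the inputs stand and 17 per group is kept, replace the 80% claim. State either that power is about 55% for a difference of 1.4 between fentanyl and fascia iliaca, or that 80% power applies to a difference of about 1.8–1.9. If 80% power for 1.4 is to be kept instead, the group size has to be 29–30.
3. As a separate clarification on which the finding does not depend, add a sentence saying that the calculation covers fentanyl versus fascia iliaca and not the PENG versus fascia iliaca hypothesis. The protocol gives no PENG SD. If it is assumed to lie between 0.9 and 2.5, with the fascia iliaca SD at 0.9, the difference detectable with 80% power at 17 per group is about 0.9 to 1.9.

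The cost is one check and one corrected paragraph. No extra patients are needed unless the sponsor chooses to restore 80% power. If the inputs stand and 17 is kept, the stated power becomes less favourable.
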